The Parental Reflective Functioning Questionnaire (PRFQ) will be used to assess parental reflective functioning. The PRFQ has not been validated by developers for parents of children aged six to eleven (Luyten et al., 2017). However, there is preliminary evidence that the measure is valid in children up to the age of ten (Pazzaglia et al., 2018). Consequently, the PRFQ will be used for participants of this study as, despite the limited validation in age range of the PRFQ, it is the only measure in existence that captures parental reflectivity.

Ideographic measure

An ideographic measure is included to capture parents' perception of the problems and assess any change. The Psychological Outcomes Profiles (PSYCHLOPS; Ashworth et al., 2009) items will be generated with each participant at the beginning of the baseline phase. The PSYCHLOPS is more proportionate than the Personal Questionnaire (Elliott et al., 2016) as it focuses on two problem areas rather than ten; this will reduce the time burden on participants during the generation of items and completion of the measure.

General wellbeing measure

Understanding general wellbeing is important as it is likely to impact parenting behaviour. The Short Warwick-Edinburgh Mental Well-Being Scale (SWEMWBS; Tennant et al., 2007) will be used instead of the General Health Questionnaire (GHQ-12; McCabe et al., 1996) because the GHQ-12 primarily screens for psychopathology whereas the SWEMWBS also captures positive aspects of wellbeing.

Change interview

One month post intervention the participants will also be asked to take part in a semi-structured change interview (Rodgers & Elliott, 2015). The purpose of the interview is to capture parents' views of any changes resulting from their participation in the NHA intervention. The addition of this qualitative data will allow for a more comprehensive evaluation of the intervention.

STUDY DESIGN

The study proposes using a non-concurrent across-participant multiple baseline A-B single case design. The baseline period (A) precedes the intervention period (B), where the NHA is delivered in a guided self-help format over six weeks. Data will be collected using psychometric measures and post-intervention data

collection will also include a qualitative semi-structured change interview. Full details are given below in "Study Procedure".

DATA ANALYSIS

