Visual analysis is the suggested method of analysing single case design data (Barlow et al., 2009) and consequently will be used to analyse the data resulting from this research. The data will be visually represented on graphs and examined for trends in the data indicating if and when change has occurred across the process measures for the three variables of interest. The data will also be analysed to establish if any changes are reliable and clinically significant. Assessment of reliable change identifies if change is genuine or resulting from measurement error; this will be calculated using the Reliable Change Index (Jacobson & Truax, 1991). If changes prove reliable, they will be analysed for clinical significance (Jacobson & Truax, 1991). The change interviews will be transcribed verbatim by the doctoral student and analysed using framework analysis as outlined by Gale et al. (2013). NVivo will be used to conduct the framework analysis.

Data analysis will be completed by the doctoral student with support from the research supervisors (CI and collaborator). No interim analysis are planned.

STUDY SETTING

The study will be run across two mental health trusts in the East Midlands. The specialist children's services (Child and Adolescent Mental Health Service; CAMHS) within [redacted NHS Trust] will be the primary study site. The CAMHS service consists of four locality teams across the county, all of which work together to form one service. The population being recruited from will be parents/carers of children on the waiting lists for these services. Recruitment will be supported by staff within these services who are aware of the research project and its aims.

The secondary study site will be CAMHS services within [redacted NHS Trust]. Recruitment will only occur in the secondary study site if it has not been possible to recruit sufficient participants from the primary study site. Again, recruitment will be focused on parents/carers of children on the waiting lists for CAMHS services and will be supported by clinical psychologists within CAMHS who are aware of the research project and its aims.

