The intervention phase will exclusively use the official NHA self-help workbook (Glasser, 2016); a workbook will be purchased for each participant by the research team using the research budget. The doctoral student will also undertake the six-hour NHA online training course produced by the creators of the NHA (Glasser & Easley, 2016). This is to ensure that the guided aspect of the intervention is completed with as much fidelity to the approach as possible.

A chapter from the book will be sent to the participants each week through the post. Each participant will be requested to read the chapter prior to the arranged guided self-help session. The doctoral student will then contact the participant by phone to complete the guided self-help session which involves discussing the prompt questions provided in the workbook. The exact timing of phone calls will be organised with each participant based around their availability, the availability of the doctoral student and when they received the workbook in the post. Process measures will be collected at the beginning of this phone call. These sessions will be audio-recorded.

If participants do not read the chapter in advance of the phone call, the option will be given to the participant to read through the chapter jointly during the call, including prompt questions, or to postpone the phone call by a day. Flexibility will be prioritised as the time-intensive nature of the intervention is recognised. However, if participants do not attend the six intervention sessions, they will be withdrawn from the study as they will not be receiving the intervention in a standardised way.

One month post intervention, the participants will be contacted again to complete all five measures and arrange the change interview. The measures will be completed by the doctoral student. The change interview will be completed by a second doctoral student who will not previously have been involved in the study; this interview will also take place via phone and will be audio-recorded.

Frequency of measure collection

Measure	Baseline (A)						Intervention (B)												Follow-up
	Week 1		Week 2		Week 3		Week 4		Week 5		Week 6		Week 7		Week 8		Week 9		Week 13
	Day 1	Day 4	Day 1	Day 4	Day 1	Day 4	Day 1	Day 4	Day 1	Day 4	Day 1	Day 4	Day 1	Day 4	Day 1	Day 4	Day 1	Day 4	Day 1
Short Warwick-Edinburgh Mental Wellbeing Scale (SWEMWBS)	✓																	✓	✓
Psychological Outcomes Profiles (PSYCHLOPS)	✓																	✓	✓

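### PSYCHLOPS is read once before the intervention, on the first baseline call, so its change to Week 9 or Week 13 includes the untreated baseline weeks

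*Combined protocol and SAP*

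**What the plan says.** The design is A-B: a baseline phase of nominally three weeks, then six weeks of guided self-help, then follow-up four weeks later (Study Summary; Study Design).

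Under Secondary Endpoints/Outcomes, the ideographic measure is included to capture parents' "perception of the problems and assess any change". Its "items will be generated with each participant at the beginning of the baseline phase". It was preferred to a longer alternative because "this will reduce the time burden on participants during the generation of items and completion of the measure".

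In the table headed Frequency of measure collection (Study Regimen), the row for "Psychological Outcomes Profiles (PSYCHLOPS") has ticks at Week 1 Day 1, Week 9 Day 4 and Week 13 Day 1 only. The Short Warwick-Edinburgh scale (SWEMWBS) has the same three ticks. The BPM, the parenting scale (MAPS) and the reflective functioning questionnaire (PRFQ) each have six baseline, six intervention and one follow-up reading.

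Data Analysis plans a visual examination for trends "indicating if and when change has occurred across the process measures for the three variables of interest". It then adds: "The data will also be analysed to establish if any changes are reliable and clinically significant". That second sentence names no measures and no pair of time points.

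**The concern.** In an A-B design the baseline phase shows what happens without the intervention. A single reading on the first day of that phase shows neither trend nor stability, and it is the reading furthest in time from the start of the intervention.

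If a parent's PSYCHLOPS score improves between Week 1 and Week 9, the improvement could have occurred before the first chapter was sent, and the PSYCHLOPS data could not show otherwise. The two quantitative methods do not help. The visual dating of change is tied to the repeated process measures. The Reliable Change Index, if applied to PSYCHLOPS, asks whether a change exceeds measurement error, not whether it came before or after the intervention began.

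What is at stake is the reading of one secondary measure: change from Week 1 could be credited to the intervention when part or all of it belongs to the baseline weeks. The change from Week 9 to Week 13 is not affected.

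**Working it through.** **Inputs**
- Phase lengths: 3 weeks baseline, 6 weeks intervention, 4 weeks to follow-up (Study Summary, Study Duration). Check against the stated total: 3 + 6 + 4 = 13 weeks, which agrees.
- PSYCHLOPS readings: Week 1 Day 1, Week 9 Day 4, Week 13 Day 1 (Frequency of measure collection).
- Last scheduled baseline call: Week 3 Day 4. Intervention phase: weeks 4 to 9. First intervention call with measures: Week 4 Day 4.
- The participant flowchart allows the baseline to run somewhat beyond three weeks but gives no figure. Call dates are flexible.

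**Day offsets**, with Week 1 Day 1 as day 0: (week − 1) × 7 + (day − 1)
- Week 3 Day 4: 2 × 7 + 3 = 17
- Week 4 Day 1: 3 × 7 + 0 = 21
- Week 4 Day 4: 3 × 7 + 3 = 24
- Week 9 Day 4: 8 × 7 + 3 = 59
- Week 13 Day 1: 12 × 7 + 0 = 84

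**Untreated share** = days from the pre score to the start of the intervention ÷ days from the pre score to the later reading.

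| Case | To Week 9 | To Week 13 |
|---|---|---|
| Nominal schedule, start at Week 4 Day 1 | 21/59 = 35.6% | 21/84 = 25.0% |
| Start counted from Week 4 Day 4 | 24/59 = 40.7% | 24/84 = 28.6% |
| Later call 3 days late (assumed) | 21/62 = 33.9% | 21/87 = 24.1% |
| Later call 3 days early (assumed) | 21/56 = 37.5% | 21/81 = 25.9% |
| Baseline one week longer (assumed) | 28/66 = 42.4% | 28/91 = 30.8% |
| Baseline two weeks longer (assumed) | 35/73 = 47.9% | 35/98 = 35.7% |

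**With a pre score on the last baseline call**

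| Case | To Week 9 | To Week 13 |
|---|---|---|
| Start at Week 4 Day 1 | (21 − 17)/(59 − 17) = 4/42 = 9.5% | (21 − 17)/(84 − 17) = 4/67 = 6.0% |
| Start counted from Week 4 Day 4 | (24 − 17)/(59 − 17) = 7/42 = 16.7% | (24 − 17)/(84 − 17) = 7/67 = 10.4% |

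A baseline one week longer leaves the first row unchanged, because the last baseline call moves with it: (28 − 24)/(66 − 24) = 4/42 and (28 − 24)/(91 − 24) = 4/67.

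**Added completions** for six participants: PSYCHLOPS 3 × 6 = 18 becomes 4 × 6 = 24, so 6 more. If SWEMWBS is added as well, the two together go from 36 to 48, so 12 more.

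**The case against.** The strongest reply is that this is a deliberate choice. The plan separates three repeated measures from two given at the start, the end and follow-up, and ties the dating of change to the repeated ones. It never says that PSYCHLOPS change will be dated or attributed to the intervention, and no research question names PSYCHLOPS. A comparison of Week 1 with Week 9 does assess change in the plain sense. This stands as a reason to keep the point minor. It does not answer it, because the measure was included to assess change in a study of whether the intervention works, and Week 1 Day 1 is the only pre-intervention value available.

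Second, the same parent completes the BPM six times during baseline, and the plan reviews unstable baselines case by case. A drift in perceived problems might show there. That is useful context, but the BPM is a different instrument and cannot date change in items set individually with each parent.

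Third, the change interview asks for parents' "views of any changes resulting from their participation in the NHA intervention". That addresses attribution, but qualitatively and in retrospect.

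Fourth, the shares depend on when the intervention is taken to start, and no posting date for the first chapter is given. That is correct. Counting from the first intervention call with measures raises the untreated days from 21 to 24, so the nominal figures are not the least favourable to the plan.

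Fifth, one later reading still leaves PSYCHLOPS with one point on each side of the intervention phase, so change during weeks 4 to 9 remains uncontrolled for time. This also stands. The added reading narrows the untreated window; it does not turn PSYCHLOPS into a repeated measure.

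**Conclusion.** The concern holds, as an optional improvement. On the nominal schedule, 36% of the interval to Week 9 and 25% of the interval to Week 13 precede the intervention phase. The shares are 41% and 29% if the start is counted from the first intervention call with measures, and higher with a longer baseline. All are shares of calendar time. The documents give no figure for drift in untreated scores, so the direction and size of any distortion are unknown. The call shifts of 3 days and the baseline extensions of one or two weeks are assumptions.

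The consequence is limited to PSYCHLOPS change measured from Week 1. The BPM, MAPS and PRFQ are unaffected. SWEMWBS shares the schedule, but the plan presents it as context ("Understanding general wellbeing is important as it is likely to impact parenting behaviour") and does not give it the stated task of assessing change, so the point weighs less there.

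**What to change.** Give PSYCHLOPS once more on the last baseline call before the first chapter is posted, which is Week 3 Day 4 for a three-week baseline. Keep the Week 1 items; do not regenerate them. State in Data Analysis that this reading is the pre score for change to Week 9 and Week 13. Report the change from Week 1 to the last baseline call beside it, descriptively, as the untreated comparison, without claiming that two readings establish stability. Add SWEMWBS on the same call only if burden allows.

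The cost is six more PSYCHLOPS completions (twelve across both measures), on a call that already takes place, plus one for each replacement participant who reaches that call. That call already carries three questionnaires, so there is some added burden. The documents need one or two more ticks in the schedule table and a sentence in Data Analysis. If the protocol is already approved, an amendment may be needed (Ethics Review and Compliance), with renewed consent from enrolled participants if the change might affect their participation (Consent).

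If the schedule is not changed, the report should say in one sentence that PSYCHLOPS change from Week 1 includes the baseline weeks. That costs nothing.

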Across both sites the referred children of participants will remain on the waiting list, with an allocated lead professional, for the duration of the intervention. Consequently, the services will retain clinical responsibility throughout the intervention. When potential participants are identified by staff from the services, in the first instance the allocated lead professional will establish if parents/carers consent to being contacted for research purposes. If consenting to the contact, the doctoral student will then contact potential participants – see Study Procedure below for full details. Staff from the service will have no further role in the research study. However, notes from the intervention sessions will be uploaded to the record of the referred child for each service meaning staff can access session notes if they have a legitimate reason to do so. This will be made clear to participants at the outset of the study.

SELECTION OF PARTICIPANTS

ELIGIBILITY CRITERIA

Participants will be parents/carers of children who have been referred to NHS children's services for behavioural problems. Participants will be recruited from waiting lists of NHS children's services as outlined above.

Inclusion Criteria

- The referred child is aged between three and eleven years old.
- The referred child is on a waiting list for an NHS children's service in the primary or secondary study site.

- The referred child's behavioural problems are one of the primary reasons for referral to the NHS service.
- The parent/carer identifies the referred child's behaviour as problematic.

NICE guidelines only recommend parent-focused interventions for behavioural problems with children aged between 3 and 11 years old (NICE, 2017). Child behavioural problems are an important focus of this research, hence the requirement for the referred child's behaviour to be one of the primary reasons for referral. The requirement for children to be on a waiting list for an NHS children's service means that the child and parent will be able to access treatment as usual regardless of this research and will retain an allocated lead professional from the service though the intervention. Finally, the parent/carer needs to identify the behaviour as problematic; otherwise, a guided self-help intervention would not be appropriate.

Exclusion Criteria

- The referred child has a diagnosis of developmental delay or learning disability.

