Multidimensional Assessment of Parenting Scale (MAPS)	✓	✓	✓	✓	✓	✓		✓		✓		✓		✓		✓		✓	✓
Parental Reflective Functioning Questionnaire (PRFQ)	✓	✓	✓	✓	✓	✓		✓		✓		✓		✓		✓		✓	✓
Brief Problem Monitor (BPM)	✓	✓	✓	✓	✓	✓		✓		✓		✓		✓		✓		✓	✓

SCHEDULE OF PROCEDURES

Procedures	Sessions			
	Screening	Baseline (weeks 1-3)	Intervention (weeks 4-9)	Follow up (week 13)
Informed consent	x			
Demographics		x		
Measure collection		x	x	x
Intervention			x	
Change interview				x

WITHDRAWAL

Participants may be withdrawn from the trial either at their own request or at the discretion of the investigator (with input from the whole research team). The participants will be made aware that this will not affect their future care. Participants will be made aware (via the information sheet and consent form) that should they withdraw the data collected to date may not be erased in accordance with the University's Research Privacy Notice and information given in the Participant Information Sheet and may still be used in the final analysis.

Participants who withdraw prior to starting the intervention will be replaced. After starting the intervention phase, replacement of participants will be considered on a case-by-case basis depending on individual circumstances. If a participant withdraws before the start of the intervention phase, they will not receive the self-help workbook, but will be made aware that they can purchase the book themselves.

ETHICAL AND REGULATORY CONSIDERATIONS

ASSESSMENT AND MANAGEMENT OF RISK

If information is disclosed during the study that could pose a risk of harm to the participant or others, the researcher will discuss this with the CI and where appropriate report accordingly.

Risks will be managed in accordance with each trust's safeguarding policy. The Health and Care Professions Council (HCPC) practitioner psychologist guidance will also be adhered to. During participation in the study, the doctoral student may become aware of harm being caused to the referred child or other children. If a disclosure or concerns about a child are raised, the trust policies will be followed and the referred child's usual care team and the chief investigator will be informed at the earliest possible opportunity.

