It is also possible that the participant will disclose that they are at risk of harm to themselves or others, or are at risk of harm from others, in which case trust policies will be followed and the child's usual care team and the chief investigator will be informed at the earliest possible opportunity.

Individual participant medical information obtained as a result of this study are considered confidential and disclosure to third parties is prohibited with the exceptions noted. Medical information may be given to the participant's medical team and all appropriate medical personnel responsible for the participant's welfare.

ADVERSE EVENTS

Due to the nature of this study no adverse events are anticipated, and no adverse event data will be collected.

ETHICS REVIEW AND COMPLIANCE

The study shall not commence until the study protocol, information sheets and consent forms have been reviewed and approved from a Research Ethics Committee and relevant NHS/Social Care permission is obtained

The sponsor will be responsible for deciding whether amendments are substantial and non-substantial in collaboration with the Chief Investigator.

Where an amendment is required to study documentation that required REC approval, changes will not be implemented until REC approval and HRA categorisation is received. Where an amendment requires local approval this shall be sought prior to the amendment be implemented at each site in accordance with the categorisation given on the HRA approval letter.

Should an amendment be required to eliminate an apparent immediate hazard to participants this may be implemented immediately and the REC/HRA and R&D will be notified as soon as possible.

Minor amendments for logistical or administrative purposes may be implemented immediately

Amendments will be logged on the Sponsor's Study Amendment Log and stored in the Trial Master/Site File(s).

Annual Progress Reports shall be submitted to the REC within 30 days of the anniversary date on which the favourable opinion was given – until the end of the study.

A final report shall (where possible) be submitted to the REC within one year after the end of the study.

If the study is terminated prematurely the CI will notify the REC, including the reasons for premature termination.

PEER REVIEW

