The study was reviewed as part of the academic requirements for the DClinPsy course that the doctoral student is undertaken. The feedback from the peer review by university academic staff is detailed in the scientific critique document.

PUBLIC & PATIENT INVOLVEMENT

Input will be sought by the service user and carer advisory panel (SUCAP) attached to the Trent DClinPsy programme. Initial input from SUCAP members shaped the formation of the research idea in the early stage of development (January 2021). Additionally, parents/carers have been consulted to check the readability and suitability of the participant information sheet, consent form and interview schedules.

PROTOCOL COMPLIANCE

Accidental protocol deviations may occur at any time. Accidental protocol deviations will be adequately documented on the relevant forms and reported to the Chief Investigator and Sponsor immediately.

Deviations from the protocol which are found to frequently recur are not acceptable, these will require immediate action and could potentially be classified as a serious breach.

DATA PROTECTION AND PATIENT CONFIDENTIALITY

All study staff and investigators will comply with the principles of the General Data Protection Regulation (GDPR) 2016/079 in protecting the rights of study participants with regards to the collection, storage, processing and disclosure of personal information and will uphold the Act's/Regulations core principles.

Each participant will be assigned a participant identification code, for use on study records, other study related documents and the electronic database. Personal data, as defined under the Data Protection Act, will include participant demographics, contact details, signed consent forms, recordings of intervention sessions and

recordings and transcripts of change interviews. Completed measures will not be personally identifiable as an anonymised participant identification code will be used.

Personal data, research data and the linking code will be stored in separate locations. When stored electronically, this will include using encrypted digital files within password protected folders and storage media. Personal information shall be stored separately to research data and will be kept secure, and maintained.

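### Adverse event data are ruled out, and nothing commits the study to recording disclosed harms, reported negative effects or reasons for withdrawal; parents who leave early are covered least

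*Combined protocol and SAP*

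**What the plan says.** The Adverse Events section is an active rule, not silence: "Due to the nature of this study no adverse events are anticipated, and no adverse event data will be collected". AE, SAE and CRF stand in the list of abbreviations, but no adverse event procedure or form is described.

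Assessment and Management of Risk expects that relevant information may arise. On children: "the doctoral student may become aware of harm being caused to the referred child or other children". On the parent: "It is also possible that the participant will disclose that they are at risk of harm to themselves or others". Both are handled under trust policy, with the usual care team and the chief investigator informed.

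Other material will exist:

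- Study Setting: "notes from the intervention sessions will be uploaded to the record of the referred child for each service".
- Study Regimen, on the guided calls: "These sessions will be audio-recorded".
- Data Analysis, on the scales: "The data will also be analysed to establish if any changes are reliable and clinically significant". The process measures are also graphed.
- Data Analysis, on the interviews: "The change interviews will be transcribed verbatim by the doctoral student", followed by framework analysis. No such step is planned for the session recordings.

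The Withdrawal section allows a parent to leave on request or at the investigator's discretion. It lets replacement after the start of the intervention be decided individually. It does not say that reasons will be recorded.

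**The concern.** Feasibility and acceptability form a stated research question, and the background describes the evidence for the approach as very thin. Why a parent stopped, and whether a parent felt the programme made things worse, bear directly on that question. If neither has a place in the study data, the report must rely on what the researcher happens to know or what completers volunteer.

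The parents most likely to be missed are those who leave after starting. The flowchart withdraws anyone who stops meeting the eligibility criteria during the intervention, and active multi-agency involvement is an exclusion criterion. A disclosure that led to such involvement could therefore end participation with no planned study record of why. With three to six families, one unrecorded case is a large share of the evidence.

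**Working it through.** The plan gives no figure on this point to reproduce. The check is of the text and the measurement schedule, followed by a calculation that bears on the fix.

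**1. Where each kind of information goes**

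| Information | Where it goes | Committed as study data? |
|---|---|---|
| Worsening on BPM, MAPS or PRFQ | Graphs; Reliable Change Index on any change | Yes, without a named deterioration category |
| Negative effects felt by a completer | Change interview at week 13 | Possibly; no harm item is stated, and the interview schedule is not in the documents |
| Safeguarding disclosure | Usual care team, chief investigator, child's clinical record | No |
| Content of guided sessions | Audio recording, clinical note | No planned extraction |
| Parent's reason for leaving | Parent informs the researcher | No commitment to ask, record or report |
| Why measures were missed | Researcher asks (Study Regimen, Baseline phase) | No commitment to record or report |

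**2. What a leaver contributes** (frequency table, Study Regimen)

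- Completer: BPM, MAPS and PRFQ 6 + 6 + 1 = 13 times each; SWEMWBS and PSYCHLOPS 1 + 1 + 1 = 3 times each.
- Leaver after session k: 6 + k of BPM, MAPS and PRFQ, so 7 for k = 1 and 11 for k = 5.
- For k below 6: one SWEMWBS and one PSYCHLOPS score, so no change can be computed on either, and no week 13 interview would be expected.

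The 13 and 6 + k are scheduled minimums, because the flowchart allows a baseline slightly longer than three weeks. Process measures are taken at the start of each call, so the last score after session k follows k − 1 guided discussions (0 for k = 1, 4 for k = 5). It may still follow the reading of k chapters, since each chapter is to be read before its call.

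**3. How often a deterioration label would be false**

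Assumptions: two-sided 1.96 cut-off (the plan states none), hence 2.5% in the worsening direction per scale per parent; one comparison per scale; no true change. Chance of at least one false label among n parents on m independent scales: 1 − 0.975^(n·m).

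- n = 6, m = 1: 1 − 0.975^6 = 0.141
- n = 6, m = 3: 1 − 0.975^18 = 0.366
- n = 3, m = 1: 1 − 0.975^3 = 0.073
- n = 3, m = 3: 1 − 0.975^9 = 0.204

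If the scales are positively correlated, the value lies between the one-scale and three-scale figures.

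**4. What complete recording could show**

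With no harm logged, the one-sided 95% upper limit on the rate is 1 − 0.05^(1/n): 39% for n = 6 and 63% for n = 3. A log would support case description, not a claim of safety.

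**The case against.** The strongest reply is that much of this is already visible. Scores are graphed for each parent, the reliable change analysis is not limited to improvement, and the interview asks about any changes. The chief investigator hears of disclosures. Several withdrawal routes (lost eligibility, unstable baseline, missed measures, missed sessions) are known to the researcher by definition. All of that stands, and it narrows the gap to harms outside the scales, parents' own reasons, and early leavers. The unseen interview schedule may cover part of it for completers.

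Four stronger readings are tempting, and the documents do not support them.

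- A reader might infer that the plan contradicts itself by foreseeing harm while expecting no adverse events. The foreseen disclosures are safeguarding matters that may have nothing to do with the intervention, so both statements can hold.
- A reader might infer that the study could not detect worsening or say why anyone left. The graphs, the signed change scores and the known withdrawal routes rule that out.
- A reader might infer that participants are unprotected. Study Setting keeps clinical responsibility with the services, and a safeguarding pathway is described.
- A reader might infer that session recordings are set apart by their shorter retention, since the Data Protection section reads: "Personal data, as defined under the Data Protection Act, will include participant demographics, contact details, signed consent forms, recordings of intervention sessions". The same sentence goes on to include the interview recordings and transcripts, which are analysed. Retention after the study does not decide what is recorded during it.

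**Conclusion.** The concern holds as a gap in recording and reporting, of minor to moderate weight. The plan rules out adverse event data, and no section commits to logging disclosures, reported negative effects or withdrawal reasons. The primary analysis is unaffected. What suffers is the answer on acceptability and any statement about harm, mainly for parents who start the intervention and leave before the week 9 call.

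This rests on the protocol text alone; a suitable item in the interview schedule would narrow the gap for completers but not for early leavers. The measurement counts assume the scheduled three-week baseline, and the false-label figures assume the 1.96 cut-off.

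**What to change.** 1. Replace the Adverse Events sentence with: *Safeguarding disclosures and escalations, participant-reported negative effects, and reasons for withdrawal (or a note that none was given) will be logged as study data under the participant code, with date and phase, without assuming that the intervention caused them.* How disclosures are handled does not change.

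2. Report every participant who started the intervention, including any later replaced, as reliably improved, unchanged or reliably deteriorated on each scale to which the Reliable Change Index is applied, including the BPM, MAPS and PRFQ. Fix one comparison before data are seen, for example last baseline score to week 13. Because the MAPS is to be shortened for repeated use, compare the same form at both points. For leavers, use the last available score, give its session number, and say that it preceded that call's discussion. State change as missing where there is no second score.

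3. Reconcile Recruitment, which seeks consent to use a leaver's data where appropriate, with Withdrawal, which says the data may still be used. State one rule, and report how many participants' data could not be used.

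4. State the cut-off, describe harms case by case, and do not treat a single deteriorated label as proof of harm.

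The cost is a short log and one reporting category, with no new staff, visits or scales. The protocol, and possibly the information sheet and consent form, would need amending, which may have to wait for ethics approval. With three to six families, logged events need care to stay unidentifiable.
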